6.3.1.1. Female Subjects

Female subjects are considered of non-childbearing potential if they meet one of the following criteria:

- No menses for 12 or more months without an alternative medical cause. A high follicle stimulating hormone (FSH) level in the postmenopausal range may be used to confirm a postmenopausal state in women not using hormonal contraception or hormonal replacement therapy. However, in the absence of 12 months of amenorrhea, a single FSH measurement is insufficient.
- Permanently surgically sterile (bilateral oophorectomy, i.e. surgical removal of ovaries, bilateral salpingectomy, or hysterectomy, i.e. surgical removal of uterus).

All other female subjects are considered to be of childbearing potential (WOCBP) and must use one of the following highly effective methods of birth control prior to the first dose of IP, during the clinical study and for at least 35 days after the last dose of IP:

- Combined (estrogen and progesterone containing) (oral, intravaginal, transdermal) hormonal contraception associated with inhibition of ovulation plus a barrier method.
- Progesterone-only hormonal (oral, injectable, implantable) contraception associated with inhibition of ovulation plus a barrier method.
- Intrauterine device.
- Intrauterine hormone-releasing system.
- Bilateral tubal occlusion.

- Sexual abstinence defined as refraining from heterosexual intercourse during the entire period of risk associated with the study treatments. The reliability of sexual abstinence needs to be evaluated in relation to the duration of the clinical study and the preferred and usual lifestyle of the subject.

Periodic abstinence (e.g. calendar, symptothermal, post-ovulation methods), declaration of abstinence for the duration of a clinical study, withdrawal, spermicides only, and lactational amenorrhea method are not acceptable as methods of contraception.

In case a WOCPB has a vasectomized partner, provided that partner is the sole sexual partner of the WOCPB clinical study participant and that the vasectomized partner has received medical assessment of the surgical success, then she is not required to use an additional form of contraception.

Within these limits, the specific forms of contraception employed are left to the discretion of the subject, the investigator, and/or the subject's physician.

The safety of GLPG3970 during breastfeeding is unknown. Nursing women are not allowed to take part in this clinical study.

6.3.1.2. Male Subjects

Non-vasectomized male subjects with female partners of childbearing potential must be willing to use a condom from the time of the first dose of IP, during the clinical study, and for at least 7 days after the last dose of IP, in addition to having their female partner use one of the following forms of contraception:

- Intrauterine device.
- Intrauterine hormone-releasing system.
- Combined (estrogen and progesterone containing) hormonal contraception associated with inhibition of ovulation (oral, intravaginal, transdermal).
- Progesterone-only hormonal contraception associated with inhibition of ovulation (oral, injectable, implantable).

Sexual abstinence defined as refraining from heterosexual intercourse is considered a highly effective contraceptive measure only if it is the preferred and usual lifestyle of the subject. The reliability of sexual abstinence needs to be evaluated in relation to the duration of the clinical study.

Periodic abstinence (e.g. calendar, symptothermal, post-ovulation methods), declaration of abstinence for the duration of a clinical study, withdrawal, spermicides only, and lactational amenorrhea method are not acceptable methods of contraception.

In a case where the female partner of a male subject has undergone documented surgical sterilization that was performed more than 1 year before screening, then the subject is not required to use an additional form of contraception.

Vasectomized male subjects with female partners of childbearing potential are not required to use an additional form of contraception providing that surgical sterilization has been successful (documented azoospermia by semen analysis).

No sperm donation is allowed from the first dose of IP during the clinical study until 7 days after the last dose of IP.

6.3.2. Prior and Concomitant Medications

Prior and concomitant therapies taken for long-term treatment of pre-existing conditions are allowed, provided they are in accordance with the inclusion and exclusion criteria (see Section 6.1 and Section 6.2, respectively) and with the prohibitions and restrictions listed below.

In case additional concomitant medications need to be administered or dose adjustments for pre-existing conditions (except for active pSS) are needed during the study, the risk/benefit to the subject should be carefully assessed by the sponsor's medical leader and consideration given to the timing of any necessary introduction of new medications.

If during the study, the subject's condition necessitates the use of prohibited medication, the use of IP may be interrupted, preferably after consultation with the sponsor's medical leader. Re-introduction of IP can be considered after the treatment course with the prohibited medication has been stopped, and after consultation with the sponsor's medical leader.

During the study, subjects will be instructed to record any change in concomitant medication in a diary (see Section 8.8.6).

Permitted Medications

Permitted medications at screening and during the study include:

- Subjects already on treatment should be on stable SoC for at least 4 weeks prior to first IP dosing.
The following medications are permitted:
 - Corticosteroids, at a dose of ≤ 7.5 mg/day prednisone or equivalent (see [Appendix 1](#) for prednisone conversion table); AND/OR
 - NSAIDs; AND/OR
 - One single antimalarial at a stable dose (hydroxychloroquine ≤ 400 mg/day, quinacrine 100 mg/kg/day, or chloroquine ≤ 250 mg/day); AND/OR
 - One single immunosuppressant at a stable dose (MTX ≤ 10 mg/week or AZA ≤ 2 mg/kg/day); AND/OR
 - One single cholinergic stimulant at a stable dose (e.g. pilocarpine, cevimeline).
- Analgesics, other than NSAIDs, up to the maximum recommended doses may be used for pain if required.
- Medications prescribed for the treatment of comorbidities and which are not described as prohibited medications.

All doses should remain as stable as possible until the end of the study.

Rescue Medication

Rescue medication that is permitted for the treatment of acute episodes during the study include:

- In case of symptoms worsening, increase of disease activity or acute episodes, subjects and/or investigators will have the ability to treat accordingly in order to maintain the clinical integrity of the patients.
- The dosage of corticosteroids can be increased to 10 mg/day for 3 days and must be decreased to the previous dose (<=7.5 mg/day) within 7 days.

Prohibited Medications

Prohibited medications during the study include:

- MMF within a week prior to screening.
- Cyclosporine/Tacrolimus within a week prior to screening.
- Ocular medicines (e.g. topical cyclosporine, topical NSAIDs/corticosteroids) for at least 4 weeks prior to screening, except for a sporadic use defined as a course of 7 days and no more than 2 courses during the study administered 2 weeks apart.
- Cyclophosphamide within 6 months prior to screening.
- Biologics such as, but not limited to rituximab, abatacept, and any other unapproved biologic within 6 months prior to screening.
- Any other investigational medication within 3 months or 5 half-lives of the IP, whichever is longer, prior to first IP dosing.
- Anticholinergic agents or any other medication known to cause dry mouth/dry eyes that, in the opinion of the investigator, are a contributing factor to the subject's dryness. All medications that in the opinion of the investigator are not a major factor in causing dry mouth/dry eyes can be used but must be stable for at least 4 weeks prior to first IP dosing and kept stable during the course of the study.

Other Prohibited Medications and Dietary/Herbal Products:

The following medications should be discontinued at least 2 weeks or 5 half-lives of the drug, whichever is longer, prior to first IP dosing and throughout the study.

–

■

Additional Guidance for the Use of Concomitant Medication:

— [REDACTED]
■ [REDACTED]
■ [REDACTED]
The lists provided in [Appendix 2](#) through [Appendix 6](#) are non-exhaustive.

In case of questions on concomitant medications, the contract research organization (CRO)'s medical monitor (as per study contact list) and sponsor's medical leader can be contacted.

Vaccines

Live attenuated vaccines (including live attenuated Covid-19 vaccines) are prohibited in this study from 60 days prior to screening until 6 weeks after last GLPG3970 administration. Routine household contact with persons vaccinated with live vaccine components should also be avoided.

Non-live vaccines (including any non-live Covid-19 vaccines) can be administered according to local vaccination standards whenever medically appropriate. Any vaccination administration during the study should be recorded in the eCRF as a concomitant medication; all vaccine information should be collected, including brand name, manufacturer (and lot number if available) as well as administration dates. Covid-19 vaccination status should also be recorded.

6.3.3. Food and Beverage Restrictions

During the treatment and FU period, subjects must come for the study visits in the morning. At Visit 1, 4, and 5, subjects need to come for the study visits in a fasting state (no food intake for at least 8 hours) as specified in the Schedule of Activities in [Section 8.11](#).

At Visit 1 (Day 1), the IP will be administered in a fasted state. Breakfast will be provided to the subject 0.5-1 hour after the IP intake. Lunch should be eaten 1 hour before or after the ECG measurement at 4.5 hours postdose.

At all other dosing days (including Visit 2, 3, 4, and 5), the IP should be taken in a fed state (together with a meal). Subjects will refrain from the consumption of [REDACTED] beginning 48 hours prior to administration of the initial dose of IP, throughout the study until 7 days after the last IP administration.

6.3.4. Other Prohibitions and Restrictions

Intravenous immunoglobulin (IVIG) therapy will not be allowed within 24 weeks prior to screening.

6.4. Treatment Discontinuation (Temporarily and Permanently), Subject Withdrawal and Study Termination

A subject may be withdrawn from the clinical study at any time without the subject's consent if the investigator or sponsor determines that it is not in the best interest of the subject to continue

participation. In such case, the reason for withdrawal will be documented in the source documents, and the subject will be asked to complete the early discontinuation (ED) visit, and FU visit(s) for safety assessments.

Treatment with IP must be discontinued by the investigator (who may consult the sponsor's medical leader) for any of the following conditions:

- Life-threatening adverse event (AE) or a serious adverse event (SAE) that places the subject at immediate risk.
- Serious infections deemed related to study treatment by the investigator, and requiring parenteral antimicrobial therapy and/or hospitalization.
- Confirmed pregnancy or lactation.
- Subjects not meeting all inclusion criteria (e.g. ESSDAI score ≥ 5 ; see also Section 6.1) and/or subjects meeting 1 of the exclusion criteria (e.g. creatinine clearance < 60 mL/minute using Cockcroft-Gault formula; see also Section 6.2), as determined by the central laboratory results of Visit 1 (Day 1). Before discontinuing treatment with IP based on the Visit 1 (Day 1) central laboratory results, the sponsor's medical leader should be consulted.
- Subjects presenting with signs and symptoms of SARS-CoV-2 infection should immediately contact the site investigator, who should inform the sponsor's medical responsible as soon as possible, and report an AE/SAE as applicable. In case of suspected SARS-CoV-2 infection RT-PCR and serology tests should be performed to confirm the infection. The investigator, preferably after consultation with the sponsor's medical responsible, must discontinue the subject from the study. The subject could be tested for SARS-CoV-2 in facilities outside the study site and if so, the subject should be instructed to immediately inform the study investigator if the test is positive and test results should be shared with the investigator as soon as possible.
- Arrhythmia or conduction abnormality, including but not limited to prolonged QTcF, where the severity is categorized as Common Terminology Criteria for Adverse Events (CTCAE) Grade 3 or higher (QTc > 500 ms and/or 60 ms over baseline on at least 2 separate ECGs 5 minutes apart) or clinically significant arrhythmia of any grade.
- Liver enzyme increase (see also [Appendix 15](#))
 - AST and/or ALT ≥ 8 times the ULN.
 - AST and/or ALT elevations ≥ 3 times ULN with signs of liver damage (i.e. with the appearance of fatigue, nausea, vomiting, right upper quadrant pain or tenderness, fever, rash and/or eosinophilia [$> 5\%$], and/or total bilirubin ≥ 2.0 times ULN or international normalized ratio [INR] > 1.5).
 - In addition, a dose interruption or reduction (if applicable) should be considered if AST and/or ALT ≥ 3 times ULN and < 5 times ULN and dosing with IP should be interrupted if AST and/or ALT ≥ 5 and < 8 times ULN.

For subjects having:

- AST or ALT ≥ 8 times ULN.
- AST or ALT ≥ 3 times ULN with signs of liver damage (i.e. with the appearance of fatigue, nausea, vomiting, right upper quadrant pain or tenderness, fever, rash, and/or

eosinophilia [>5%], and/or total bilirubin $\geq 1.5 \times \text{ULN}$ or INR > 1.5). These cases should be reported as SAEs.

the following steps will need to be performed by the investigator:

- The site should immediately contact the subject and require the subject to discontinue IP immediately. The subject should be asked to return to the site within a 48-hour window from awareness of the result.
- A full evaluation of various causes of hepatitis should be conducted (i.e. infectious, alcohol, medications, anatomical).
- An assessment of other concomitant medications and SoC should be made. The investigator should consider to whether it is in the best interest of the subject to stop/interrupt concomitant medications and SoC treatment.
- A detailed history including relevant information on alcohol use, recreational drug use, supplement consumption, any herbal remedies, family history, sexual history, travel history, history of contact with a jaundiced subject, surgery, occupational history, blood transfusion, history of liver or allergic disease, and any other potential causes attributable to a liver insult should be collected.
- A detailed assessment of the subject's clinical condition and repeat laboratory tests for liver function test (LFT), including albumin, creatine kinase, total bilirubin (direct and indirect), gamma-glutamyl transferase (GGT), INR, and alkaline phosphatase should be done.
- Further testing for hepatitis A, B, and C, and for autoimmune hepatitis should be done. Other causes of viral hepatitis (cytomegalovirus or Epstein-Barr virus, etc) should be excluded. Liver imaging should be considered.
- Referral to a hepatologist or gastroenterologist should be requested.

Every effort should be made to keep subjects in the study and on treatment. However, the investigator, who may consult the sponsor's medical leader, can consider stopping the study treatment in case of concerns about the subject's safety, serious or severe AEs or worsening of the disease condition, which in the investigator's opinion needs an alternative treatment approach not being covered in the clinical study (e.g. rescue medication).

When study treatment is discontinued, the subject will be requested to complete the assessments of the ED visit and to return for the FU visit. Reason for discontinuation must be documented in the case report form (CRF).

Subjects will be informed prior to clinical study entry that they are allowed to withdraw from the clinical study. At any time and for any reason, a subject's participation in the clinical study may terminate at their request, without prejudice to their future medical care. The subject will be encouraged to share the reason(s) for withdrawal so this can be documented in the source documents, and to complete the ED visit and FU visit for safety assessments, but will not be obliged to do so.

Subjects who withdraw from the clinical study without contact with the site (lost-to-FU) should be contacted by the site so that their health status can be assessed and documented in the source documents. The site should make every effort to understand whether the subject is alive, including checking the medical records and contacting general practitioner or relatives, if necessary. All attempts must be documented in the source documents.

The sponsor has the right to terminate the clinical study at any time and for any reason.

The sponsor and/or investigator will discontinue the study if:

- Judged necessary for medical, safety, regulatory, or other reasons consistent with applicable laws, regulations, and ICH-GCP.
- IEC/IRB and/or RA approval or favorable opinion is withdrawn, revoked, or suspended.

In the event of study termination, the investigators and relevant authorities will be informed of the reason for clinical study termination. Please also see for reference Section 12.1.2 “Clinical Study Closure Considerations”.

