Appendix 15: Algorithm for Elevated Liver Function Tests

	AST or ALT increase to				
Value Range	>=1.5x to 3xULN	>=3x to <5xULN	>=5x to <8xULN	>=3xULN with signs of liver damage ¹	>=8xULN
IP Action	Continue as planned	Reduce or interrupt IP for at least 2 weeks	Interrupt IP for at least 2 weeks	Discontinue IP ²	Discontinue IP ²
		Close observation ²	Close observation ²		
After at least 2 weeks	AST and ALT <3xULN	AST or ALT >=3xULN			
	Weekly LFTs for the first 2 weeks (biweekly for the following weeks, or more frequently at investigator's discretion)	Discontinue IP Report SAE and complete liver event page for any of abnormalities listed below ³ : - AST/ALT increase >=3xULN with signs of liver damage ¹			

¹ Signs of liver damage:

- total bilirubin >=2.0xULN OR INR >1.5, and/or
- symptoms: appearance of fatigue, nausea, vomiting, right upper abdominal quadrant pain or tenderness, fever, rash and/or eosinophilia (>5%)

² Close observation recommendations:

- Monitor 2 to 3 times per week all of the following parameters: ALT, AST, alkaline phosphatase, total bilirubin, eosinophils, INR. If local regulations allow, home visits can be performed if subjects cannot come to the clinical study center.
- Frequency of retesting can be reduced to once a week or less if abnormalities stabilize or the IP has been discontinued; however, monitoring might still be needed more frequently taking into consideration the SoC and/or changes to this.
- Based upon investigator's discretion gastroenterology or hepatology consultations, additional serology testing, imaging, and pathology assessments may be required.
- Re-query history of symptoms, prior and concurrent diseases, concomitant medication and non-prescription medicines, herbal, dietary supplements, alcohol use, recreational drug use, special diets.

- Rule out all of the following: acute viral hepatitis, autoimmune hepatitis, alcoholic hepatitis, non-alcoholic fatty hepatitis, hypoxic/ischemic hepatitis, biliary tract disease, and cholestasis.

- Re-query exposure to environmental chemical agents.

³ The following steps should be followed:

- The site should immediately contact the subject and require the subject to discontinue IP immediately. The subject should be asked to return to the site within a 48-hour window from awareness of the result.
- A full evaluation of various causes of hepatitis should be conducted (i.e. infectious, alcohol, medications, anatomical).

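### Protocol Section 6.4 and Appendix 15 give different IP rules for AST/ALT elevations without signs of liver damage, and the text does not say which governs

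*Protocol*

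**What the plan says.** Protocol Section 6.4 introduces its stop list with "Treatment with IP must be discontinued by the investigator (who may consult the sponsor's medical leader) for any of the following conditions". The liver entry opens "Liver enzyme increase (see also" and links to Appendix 15. Two liver findings require a stop: AST and/or ALT at 8 × ULN or above, and 3 × ULN or above with signs of liver damage. For 3 to below 5 × ULN, the text is "a dose interruption or reduction (if applicable) should be considered". For 5 to below 8 × ULN, it is "dosing with IP should be interrupted if AST and/or ALT". Section 6.4 gives no duration, no recheck and no consequence if the enzymes fail to recover.

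Appendix 15 handles the same ranges as an algorithm. Its IP action for 3 to below 5 × ULN is "Reduce or interrupt IP for at least 2 weeks", with close observation. For 5 to below 8 × ULN it is interruption for the same minimum period. After at least 2 weeks the table branches. If the value is "AST or ALT >=3xULN", IP is discontinued. The close-observation footnote begins "Monitor 2 to 3 times per week all of the following parameters".

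**The concern.** Section 6.4 treats action in the lower band as something to weigh up, and Appendix 15 treats it as an instruction. Appendix 15 also contains a stop for non-recovery that the 6.4 list lacks. A cross-reference worded as an additional place to look does not settle which text prevails. This applies to patients with no symptoms and normal bilirubin and INR, so it is separate from any question about the bilirubin cut-off.

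Three things depend on which passage a site follows:

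- **Exposure.** A patient with a persistent elevation could be dosed on or discontinued.
- **Safety counts.** SAP Section 6.3.1.8 tabulates TEAEs leading to IP interruption and to IP discontinuation. Under Protocol Section 8.5.2 a laboratory abnormality is an AE only if judged clinically significant. Section 11.1.5 requires recording when it leads to a change in IP and meets the AE definition. The passage followed can therefore influence whether an asymptomatic elevation is recorded as an AE at all, and TEAEs are a primary endpoint.
- **Efficacy data.** SAP Section 3 handles early treatment discontinuation by the hypothetical strategy. SAP Section 4.4.1.2 drops non-PK data collected more than 7 days after the last dose from the on-treatment visits.

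**Working it through.** The plan states no figure to reproduce. The check sets the two passages side by side and then follows one patient through each.

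| AST/ALT finding, no signs of liver damage unless stated | Section 6.4 | Appendix 15 | Agree? |
|---|---|---|---|
| ≥3 to <5 × ULN | Consider interruption or reduction | Reduce or interrupt for at least 2 weeks | No |
| ≥5 to <8 × ULN | Interrupt, no duration | Interrupt for at least 2 weeks | Action yes, duration only in Appendix 15 |
| Still ≥3 × ULN after at least 2 weeks | No mandatory stop | Discontinue | No |
| ≥8 × ULN, or ≥3 × ULN with signs of liver damage | Discontinue | Discontinue | Yes |

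Worked case (an assumed patient): ALT 4 × ULN at Visit 2 (Day 8), no symptoms, normal bilirubin and INR, value unchanged afterwards. Visit days come from the Schedule of Activities (8, 29, 57, 85). Action is assumed to follow on the sampling day; any wait for the central laboratory result shortens the differences slightly.

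1. Section 6.4 read alone: dosing may continue to Day 85.
2. Appendix 15, interruption at once: the last dose is Day 8. Difference = 85 − 8 = 77 dosing days.
3. Appendix 15, reduction first, then stop at a recheck exactly 2 weeks later: 8 + 14 = Day 22. Difference = 85 − 22 = 63 dosing days. The 2 weeks are a minimum, so a later recheck makes this smaller.
4. Testing: the next scheduled laboratory visit after Day 8 is Day 29, a gap of 29 − 8 = 21 days. Appendix 15 recommends 2 to 3 tests a week, so 4 to 6 over the first 2 weeks (2 × 2 and 3 × 2). It allows once a week or less if values stabilise or IP is discontinued.
5. ESSDAI data: with a last dose on Day 8, the 7-day rule ends at 8 + 7 = Day 15, so none of the Week 4, 8 or 12 values (Days 29, 57, 85) is used. With a last dose on Day 22, it ends at 22 + 7 = Day 29, so Week 4 can be used but Weeks 8 and 12 cannot. If dosing continues under 6.4, all three are used. The planned active arm has 20 subjects, so one such patient there is 1/20 = 5% of it.

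**The case against.** The strongest reply is that these are parts of one protocol, linked at the very item in question. A site that follows Appendix 15 breaches nothing in 6.4: reducing or interrupting is one way of having considered it, and 6.4 lets the investigator stop treatment over safety concerns. On this view 6.4 is an incomplete summary of the algorithm it cites. That largely stands in one direction. It does not stand in the other: a site that keeps to the wording of 6.4 can depart from Appendix 15 and still claim compliance. Section 6.4 also asks that patients be kept on treatment where possible.

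A reader might infer stronger conclusions, which the documents do not support:

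- **That 6.4 tells sites to keep dosing.** It permits this and does not require it.
- **That 77 days is the typical effect, or that the choice is between intensive testing and none.** The 77 days need immediate interruption, and both passages also allow reduction. The frequent testing is a recommendation that may be relaxed, and Protocol Sections 8.2, 8.5 and 8.5.2 provide for unscheduled visits and extra laboratory tests.
- **That this band produced the liver signal, or that the reported counts are distorted.** SAP Section 1 reports termination for liver toxicity but gives no enzyme range, case count or handling.

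Two practical objections also carry weight. The Appendix 15 table was flattened in extraction, so which columns feed the 2-week branch is inferred; the matching 2-week wording in the two intermediate bands makes that reading plausible. And the SAP already plans listings of IP administration, discontinuations and flagged laboratory results, so much of the raw information will exist.

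**Conclusion.** The discrepancy is real and can be read directly from the text. It has two parts: discretionary against directive action at 3 to below 5 × ULN, and a non-recovery stop that appears only in Appendix 15 and reaches both intermediate bands. The clear split between stopping and continuing comes at the 2-week recheck, because before it both passages allow reduced dosing.

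For the assumed patient the size is about 63 dosing days if IP is reduced first, and 77 at the very most. Both figures assume detection on Day 8, an unchanged ALT and a site that relies on 6.4 alone. The documents do not show how many patients, if any, were in this position, so an effect on the results is possible but not established. The SAP's hepatotoxicity tables (Section 6.3.2.8) use cut-offs and same-day bilirubin, not persistence or action taken. On their own they will not show which rule was applied. With the study stopped, what remains is chiefly a matter of clear reporting.

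**What to change.** Reconcile Section 6.4 and Appendix 15 into one rule, either stated identically in both places or with a sentence naming which passage governs. The rule must say whether action at 3 to below 5 × ULN is required or discretionary, and whether non-recovery after at least 2 weeks is a stop. Which rule is right is for the sponsor's medical team. For any further use of this protocol text, the cost is a wording amendment.

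For this study, state the discrepancy in the CSR. Add one listing of each subject with AST or ALT at 3 × ULN or above persisting for 2 weeks or more, showing treatment group, dates and values, signs of liver damage, and the IP action taken. Take the action from the IP administration records (SAP Section 6.1.8.2, which covers reduced doses) as well as the AE page, because the action choices in Protocol Section 11.2.1 do not include a reduction. The data are already collected, so the cost is the programming of one listing.
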